4 OBJECTIVES AND ENDPOINTS

Table 4-1: Objectives and Endpoints

Objective	Endpoint
Primary	

 Prevention of Disease Progression 	
 Proportion of participants with composite end point of mechanical ventilation or death prior to or on Day 28
Secondary	

 Improvement in clinical status 	
 Change from baseline in the Ordinal 8-point Outcome Scale on Day 28

 Improvement in mortality 	
 All-cause mortality on Day 28

 Absence of critical disease 	
 Proportion of participants alive and free of respiratory failure on Day 28

 Recovery of pulmonary function 	
 Proportion of participants returned to room air by Day 28

 Shortened hospitalization 	
 Proportion of participants alive and discharged home by Day 28

 Safety 	
 Proportion of participants with SAEs and serious infections

Table 4-1: Objectives and Endpoints

Abbreviations:

SAE = serious adverse event;

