8.2 Discontinuation from the Study

Participants who request to discontinue study treatment will remain in the study and must continue to be followed for protocol specified follow-up procedures. The only exception to this is when a

participant specifically withdraws consent for any further contact with him/her or persons previously authorized by participant to provide this information.

- Participants should notify the investigator of the decision to withdraw consent from future follow-up **in writing**, whenever possible.
- The withdrawal of consent should be explained in detail in the medical records by the investigator, as to whether the withdrawal is from further treatment with study treatment only or also from study procedures and/or post treatment study follow-up, and entered on the appropriate CRF page.
- In the event that vital status (whether the participant is alive or dead) is being measured, publicly available information should be used to determine vital status only as appropriately directed in accordance with local law.
- If the participant withdraws consent for disclosure of future information, the sponsor may retain and continue to use any data collected before such a withdrawal of consent.

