8.3 Lost to Follow-Up

- All reasonable efforts must be made to locate participants to determine and report their ongoing status. This includes follow-up with persons authorized by the participant.
- Lost to follow-up is defined by the inability to reach the participant after a minimum of **three** documented phone calls, faxes, or emails as well as lack of response by participant to one registered mail letter. All attempts should be documented in the participant's medical records.
- If it is determined that the participant has died, the site will use permissible local methods to obtain date and cause of death.
- If investigator's use of third-party representative to assist in the follow-up portion of the study has been included in the participant's informed consent, then the investigator may use a Sponsor retained third-party representative to assist site staff with obtaining participant's contact information or other public vital status data necessary to complete the follow-up portion of the study.
- The site staff and representative will consult publicly available sources, such as public health registries and databases, in order to obtain updated contact information.
- If after all attempts, the participant remains lost to follow-up, then the last known alive date as determined by the investigator should be reported and documented in the participant's medical records.

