9.1.1.3 Improvement in Mortality

Mortality for this endpoint will be based on all-cause mortality at Day 28 which represent participants who are in state 1 of the Ordinal 8-point Outcome Scale.

For participants deaths, data will be collected on whether the death occurred after withdrawal of care and, if so, the reason for withdrawal of care will be recorded (eg, brain death, patient/family request, resource constraint).

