10.2 Populations for Analyses

For purposes of analysis, the following populations are defined:

Population	Description
Enrolled	All participants who sign informed consent
Intent-to-treat (ITT) Population	All randomized participants, also those randomized and never treated. This population will be used for all efficacy analysis. Analyses using the ITT analysis population will group the participants according to the treatment group to which they are randomized.

Population	Description
Per-protocol (PP) Analysis Population	The PP Population includes all randomized participants excluding the participants with relevant protocol deviations. Relevant protocol deviations are those that may potentially impact the primary endpoint. The relevant protocol deviation criteria will be defined in the statistical analysis plan. If more than 10% of subjects in either treatment group have relevant protocol deviations, the PP Analysis Population will be used for a sensitivity analysis of the primary endpoint.
As-treated Analysis Population	This population includes all randomized participants except those randomized who are not treated. Analyses using the as-treated analysis population will group the participants according to the treatment they received: abatacept or placebo. All safety analyses will use the As-treated Analysis Population.

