	
participants with no primary endpoint assessment due to withdrawal of consent or for other reasons will be imputed as treatment failures (ie. progressors). The OR along with its 2-sided 70% CI and 95% CI, as well as the absolute treatment difference in proportions with its 95% will be presented. The construction of CIs for absolute differences in proportions between treatment groups will be based on minimum risk weights⁵⁹ to account for randomization stratification factors and baseline severity.
 
A supplemental analysis of the primary endpoint comparison between the treatment groups will be based on logistic regression with age as a continuous covariate and factors for baseline severity and remdesivir stratification in the model. The nominal p-value for the Chi-square test based on this model will be presented.
 
The primary endpoint is a composite endpoint. The number and percentage of participants progressing to each of the components will be presented by treatment group.
 
The proportion and 95% CI of participants with mechanical ventilation or who died prior to or on Day 28 within treatment group as well as the difference in proportions between the treatment groups and its 95% CI will also be presented by site, age-subgroup (< 60, ≥ 60), remdesivir use (stratification factor), gender, and baseline severity.
 
Kaplan-Meier estimates for the time from randomization to progression to the primary endpoint will be presented. The p-value for the treatment comparison based on the stratified log-rank test, stratified by age-group and remdesivir use, will be presented as a sensitivity analysis of the primary endpoint.

Secondary Binary Endpoints:
	
Proportions and 95% CIs for the binary efficacy endpoints will be presented by treatment group. CIs for proportions within treatment groups will be based on normal approximation. Difference in proportions and 95% CI will be presented, as well as the nominal p-value derived from the CMH Chi-square test stratified by baseline severity and the randomization stratification factors. The construction of CIs for differences in proportions between treatment groups will be based on minimum risk weights to account for randomization stratification factors and baseline severity. A missing response value due to withdrawal of consent or for other reasons will be imputed as a non-responder or progressing.

Table 10.3.1-1: Efficacy Statistical Analyses

Endpoint	Statistical Analysis Methods

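### The missing-data rule for secondary binary endpoints makes no exception for Day 28 mortality, so vital status still unknown after follow-up would be counted as death

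*Protocol*

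**What the plan says.** Protocol Section 4 (Table 4-1) lists "All-cause mortality on Day 28" as the endpoint for the secondary objective on mortality. Section 9.1.1.3 confirms the definition ("Mortality for this endpoint will be based on all-cause mortality at Day 28") and equates it with state 1 of the ordinal scale, which makes it a yes/no outcome.

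The efficacy analysis table in Section 10.3.1 has two rows for secondary endpoints: one for binary endpoints and one for change on the ordinal scale. The binary row carries a single missing-data rule: "A missing response value due to withdrawal of consent or for other reasons will be imputed as a non-responder or progressing". Section 10.2 fixes the denominator as the ITT population of all randomized participants: "This population will be used for all efficacy analysis".

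Other sections limit how many values will be missing:

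- Section 8.2 keeps participants in follow-up after they stop treatment. Where vital status is measured, "publicly available information should be used to determine vital status only as appropriately directed in accordance with local law".
- Section 8.3 requires repeated contact attempts and a search of public sources. If these fail, "then the last known alive date as determined by the investigator should be reported and documented".
- Section 10.3 says that post-discharge data will be considered for the analyses.

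**The concern.** The rule is a normal failure convention for the other three secondary binary efficacy endpoints (free of respiratory failure, on room air, discharged home). Scoring an unknown result there as a non-response is conservative and easy to explain. Mortality is different. The unfavourable value is a death, and the rule would record one that nobody observed, in a participant last known to be alive.

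Three things are at stake:

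- The arm-level proportions would no longer be mortality. If deaths are infrequent, a handful of unresolved participants could make up a large share of the total.
- Unequal loss between arms would translate almost one for one into a mortality difference.
- Death counts could disagree between tables. Section 10.3.1 also asks for the number of participants reaching each component of the primary composite, and fatal events are reported as SAEs. If those tables use observed deaths, the mortality table would contain deaths found nowhere else.

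**Working it through.** **Does the rule reach mortality?** The endpoint is secondary (Section 4) and scored as state 1 or not (Section 9.1.1.3), so it is binary. The only other secondary row in Table 10.3.1-1 is for ordinal change. Mortality therefore falls in the binary row, which names no exception. The Kaplan-Meier analysis in the table is for the primary composite, and the visible text gives no separate mortality analysis.

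**Do the follow-up provisions change the scoring?** No. Sections 8.2, 8.3 and 10.3 reduce the number of missing values. They do not say how a value that stays missing is scored.

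**Inputs.** Arm sizes are 86 abatacept and 43 placebo (Section 10.1). The plan states no figure for mortality or for missingness, so there is none to reproduce for this endpoint. The sample size that supplies the arm sizes does reproduce: 25% vs 10%, one-sided 0.15, continuity-corrected, 2:1 allocation gives 43 + 86 = 129, with power 80.6%. Mortality p and the share m with unresolved vital status are assumptions. Within each arm, missingness is taken as unrelated to death.

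**Formulas.**

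- Reported mortality per arm = p + (1 − p)m
- Survivors counted as dead = m × [86(1 − p_aba) + 43(1 − p_pbo)]

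**Equal missingness, true mortality 10% placebo and 5% abatacept.** Expected true deaths are 43 × 0.10 + 86 × 0.05 = 4.3 + 4.3 = 8.6. Expected survivors are 38.7 + 81.7 = 120.4.

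| m | Reported placebo | Reported abatacept | Difference (points) | Survivors counted as dead | Share of counted deaths |
|---|---|---|---|---|---|
| 0 | 10.0% | 5.0% | −5.0 | 0 | 0 |
| 2% | 11.8% | 6.9% | −4.9 | 2.4 | 2.4/11.0 = 22% |
| 5% | 14.5% | 9.8% | −4.75 | 6.0 | 6.0/14.6 = 41% |
| 10% | 19.0% | 14.5% | −4.5 | 12.0 | 12.0/20.6 = 58% |

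For the 5% row: placebo 0.10 + 0.90 × 0.05 = 0.145; abatacept 0.05 + 0.95 × 0.05 = 0.0975; survivors counted as dead 0.05 × 120.4 = 6.02; counted deaths 8.6 + 6.02 = 14.62. The difference shrinks by the factor (1 − m): −5.0 × 0.95 = −4.75.

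**Higher mortality, 15% placebo and 7.5% abatacept, m = 5%.** True deaths are 6.45 + 6.45 = 12.9. Survivors counted as dead are 0.05 × 116.1 = 5.8. The share is 5.8/18.7 = 31%.

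**Unequal missingness, no true effect (10% in both arms).** With m = 2% placebo and 7% abatacept, reported mortality is 0.10 + 0.90 × 0.02 = 11.8% and 0.10 + 0.90 × 0.07 = 16.3%, a difference of +4.5 points. Swapping the arms gives −4.5. In general the spurious difference is 0.90 times the gap in missingness. A 5-point gap corresponds to about 4 of 86 abatacept participants or 2 of 43 placebo participants.

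**The case against.** The strongest reply is that few participants would be affected. Discharged participants are contacted about weekly to Day 60, with a Day 28 contact allowed ±2 days (Section 5.1.4). Withdrawal ends follow-up only when the participant refuses further contact, including with persons previously authorized, and even then public records are to be used as far as local law allows. This stands. A reader might infer that anyone who misses the Day 28 call is tabulated as dead, but the documents do not support that. A participant reached alive after Day 28 was alive on Day 28, so the mortality value is known. It would still help to say so, because Section 9.1.1.3 ties the endpoint to the scale state at Day 28 and does not mention later contacts.

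A second reply is that the rule never uses the word death and is phrased for responders. That is true, and the reading is an inference. But no other unfavourable value exists for this endpoint, and mortality is the only one of the four binary efficacy endpoints framed as an adverse outcome, which is where the reference to progressing fits best.

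A third reply concerns size. With equal missingness a risk ratio would move noticeably, from 0.50 to 0.67 at 5% missing (0.0975/0.145), and a reader might conclude that the treatment comparison is badly diluted. The plan does not report a ratio for these endpoints. It reports proportions and their difference, and the difference hardly changes.

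Finally, a reader might infer that faster discharge on abatacept would produce more loss, and so more imputed deaths, in that arm. Nothing in the documents gives the direction or amount of any imbalance.

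**Conclusion.** The point holds in limited form. As written, the plan scores Day 28 vital status that remains unresolved after all follow-up as a death. The follow-up provisions make such cases fewer but do not alter their scoring. The SAP is not shown and may add detail, but the protocol itself fixes this rule, and departing from it would mean contradicting the protocol.

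The main effect is inflated arm-level mortality: 14.5% and 9.8% in place of 10% and 5%, with 41% of counted deaths being survivors, under the assumed 5% missingness in each arm. The planned difference is nearly unaffected when loss is balanced and is biased by about 0.9 points per point of imbalance when it is not (at 10% true mortality in both arms). All of these figures rest on assumed mortality and missingness rates and on loss being unrelated to death within each arm. If follow-up is close to complete, the effect is close to nil.

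The consequence is modest. Only the primary endpoint is formally tested, and p-values for secondary endpoints are nominal.

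**What to change.** Amend the Secondary Binary Endpoints row of Table 10.3.1-1 so that mortality is exempt from the non-responder rule, and state that:

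1. all known vital status is used, including any contact after Day 28 that shows the participant was alive on Day 28;
2. for participants still unresolved, Day 28 mortality is estimated by arm with censoring at the last known alive date, for example by Kaplan-Meier, with the difference between arms and its CI;
3. missing-as-dead is retained as a labelled worst-case sensitivity analysis.

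The cost is a short addition to the table text and one extra output table. No new data are needed, because Section 8.3 already has the last known alive date recorded. There are two downsides. Mortality would be handled differently from the other binary endpoints. Censoring also assumes that loss is non-informative, which is open to question for participants who withdraw; the sensitivity analysis in item 3 addresses that.

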10.3.2 Safety Analyses

The proportion (%) of participants with SAEs, AEs of special interest, and participants with laboratory marked abnormalities will be provided by treatment group. Summaries will include all events from randomization up to 60 days using the as-treated analysis population. AEs of special interest are infections and infusion reactions.

10.3.4 Interim Analyses

A SOC will assist in the oversight of the study execution and ongoing assessment of safety and efficacy. The Charter for the SOC will include details on boundaries to be used for establishing early evidence of efficacy at interim analysis.

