10 STATISTICAL CONSIDERATIONS

10.1 Sample Size Determination

A 25% estimated rate of progression under placebo plus standard of care to one of the elements of the primary endpoint (mechanical ventilation or death) of hospitalized COVID-19 untreated patients (in particular patients without targeted therapy) was derived from available literature^{1,2,55,56,57,58} and anecdotal feedback. Rates of progression in these reports ranged from 8% to 32%. All reports are from China and include hospitalized patients that had respiratory symptoms. There are different definitions of progression in these reports but most are based on ICU and/or death.

A two group continuity corrected χ^2 test with a 0.150 one-sided significance level will have 80% power to detect the difference between a proportion of 10% abatacept treated participants and a proportion of 25% participants in the placebo group with a primary endpoint event (odds ratio of .33, ie, odds of progression under abatacept versus placebo) when the sample sizes are 86 and 43, respectively (a total sample size of 129). This computation was made using nQuery Advisor version 7. The target sample size for this study is approximately 129 randomized participants.

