10.3.1 Efficacy Analyses

Statistical analysis methods for efficacy analyses are provided in Table 10.3.1-1. The primary efficacy endpoint will be formally tested for difference between the treatment groups. Nominal p-values for treatment comparison will be provided for selected secondary endpoints.

Table 10.3.1-1: Efficacy Statistical Analyses

Endpoint	Statistical Analysis Methods
Primary Efficacy Endpoint	The comparison between treatment groups of the proportion of participants with primary endpoint event (mechanical ventilation or death) prior to or on Day 28 will be performed using the Cochran-Mantel-Haenszel (CMH) Chi-Square test, stratified by the randomization stratification factors age group (< 60, ≥ 60) and remdesivir use as well as baseline severity. Baseline severity will be defined by the Clinical Status scale at randomization. A one-sided significance level of 0.15 will be used to assess statistical superiority of abatacept over placebo. The ITT population will be used. Randomized

Table 10.3.1-1: Efficacy Statistical Analyses

[figure not shown]
Endpoint	Statistical Analysis Methods

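### Does the planned interim efficacy boundary push the primary test above its one-sided 0.15 level?

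*Protocol*

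**What the plan says.** - **Interim look.** Protocol Section 10.3.4 gives the SOC a role in assessing efficacy as well as safety, and adds: "The Charter for the SOC will include details on boundaries to be used for establishing early evidence of efficacy at interim analysis". The number of looks, their timing, the boundary type and the alpha spent are not given there.
- **Primary test.** Section 10.3.1 (Table 10.3.1-1) and the Synopsis both state: "A one-sided significance level of 0.15 will be used to assess statistical superiority of abatacept over placebo". The test is a stratified Cochran-Mantel-Haenszel (CMH) test. It is the only formal efficacy test; p-values for secondary endpoints are nominal.
- **Interval.** The same table has the primary result reported as "The OR along with its 2-sided 70% CI and 95% CI". The two intervals are to be presented; neither is made a criterion for success.
- **Sample size.** Section 10.1 assumes event rates of 10% on abatacept and 25% on placebo, with 86 and 43 participants (129 in all). For a chi-square with continuity correction it claims: "test with a 0.150 one-sided significance level will have 80% power to detect the difference".
- **Purpose.** Section 5.1 describes a study for detecting signals of efficacy and safety. Section 5.4 says the significance level was raised on purpose, to shorten the way to a larger study.

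**The concern.** A boundary for early efficacy gives the trial a second chance to declare success. If that chance is taken and the final test still runs at the full 0.15, the overall false-positive rate can exceed 0.15.

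Three features of the Protocol seem to point that way. The level is stated without the word overall. A 70% interval is exactly the one that pairs with an unadjusted one-sided 0.15 test (1 − 2 × 0.15 = 0.70). And the sample size is computed as a single look at 0.150, with nothing set aside.

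The level is already generous, and a positive signal is meant to speed a larger study. A further rise in the error rate would weaken the only formal efficacy test, and the 70% interval would no longer match the final decision rule.

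**Working it through.** **1. The plan's own figure.** Inputs from Section 10.1: placebo rate p1 = 0.25, abatacept rate p2 = 0.10, allocation r = 2, one-sided 0.15 (z = 1.036), power 80% (z = 0.842). The pooled rate is (0.25 + 2 × 0.10)/3 = 0.15.

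Without correction, placebo n' = [1.036 × √(3 × 0.15 × 0.85) + 0.842 × √(2 × 0.25 × 0.75 + 0.10 × 0.90)]² / (2 × 0.15²) = (0.641 + 0.574)² / 0.045 ≈ 32.8.

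With the continuity correction, n = (n'/4) × [1 + √(1 + 2 × 3/(n' × 2 × 0.15))]² ≈ 8.2 × 2.269² ≈ 42.2, rounded up to 43. So 43 + 86 = 129, as stated. Power at these numbers is 80.6% from the same formula and 80.9% by exact enumeration. The figure is right for a single look at 0.15.

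**2. What an efficacy look could do.** The Protocol gives no boundary or timing, so one look at information fraction t is assumed. Under the null the interim and final statistics Z1 and Z2 are bivariate normal with correlation √t. With interim bound b and the final test left at 1.036, the overall error is P(Z1 ≥ b or Z2 ≥ 1.036).

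Interim alpha, with 0.15 as the total:
- O'Brien-Fleming-type spending: 2 × [1 − Φ(1.440/√t)]. At t = 0.5 this is 0.0418.
- Pocock-type spending: 0.15 × ln[1 + (e − 1)t]. At t = 0.5 this is 0.0930.
- Very strict rule: 0.001 at the interim.

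| Look at | Boundary | Interim alpha | Overall error if final stays at 0.15 | Final level that holds 0.15 | Matching 2-sided CI | Power, from 80% |
|---|---|---|---|---|---|---|
| 33% | strict | 0.001 | 0.150 | 0.150 | 70.0% | 80.0% |
| 33% | O'Brien-Fleming-type | 0.0127 | 0.154 | 0.146 | 70.8% | 79.8% |
| 33% | Pocock-type | 0.0679 | 0.182 | 0.113 | 77.4% | 77.1% |
| 50% | strict | 0.001 | 0.150 | 0.150 | 70.0% | 80.0% |
| 50% | O'Brien-Fleming-type | 0.0418 | 0.161 | 0.138 | 72.4% | 79.3% |
| 50% | Pocock-type | 0.0930 | 0.186 | 0.103 | 79.4% | 76.7% |
| 67% | strict | 0.001 | 0.150 | 0.150 | 70.0% | 80.0% |
| 67% | O'Brien-Fleming-type | 0.0779 | 0.168 | 0.128 | 74.4% | 78.9% |
| 67% | Pocock-type | 0.1145 | 0.186 | 0.097 | 80.6% | 76.9% |

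The interim alpha does not simply add to 0.15, because the looks are correlated. At the mid-point O'Brien-Fleming-type look, 0.0418 is spent but the error rises by only 0.161 − 0.150 = 0.011. Most trials that cross early under the null would also have rejected at the end.

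Two unadjusted variants lie outside the table. Looks at one third and two thirds give 0.169 (O'Brien-Fleming-type) or 0.194 (Pocock-type). A mid-point look tested at the full 0.15 gives 0.221.

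**3. The planned test.** A simulation of the uncorrected stratified CMH test (86 vs 43, eight strata, 25% in both arms, look at 50%, final at 0.15) gave 0.151 for a single look, 0.164 with an O'Brien-Fleming-type look and 0.190 with a Pocock-type look. For 10% vs 25%, power was about 86% with a single look. When the looks share the 0.15, it was 85% (O'Brien-Fleming-type) or 83% (Pocock-type). Missing outcomes counted as failures were not modelled.

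**4. The sections side by side.** Section 10.3.1 names a significance level for superiority but does not call it the level of the last look. Section 10.3.4 sends the boundaries elsewhere. Take 0.15 as the trial's level, with the charter or SAP dividing it between looks, and every sentence in both sections stands. Excess error needs three things together: 0.15 meant for the last look alone, a boundary that spends more than a trivial amount, and no adjustment in either the charter or the SAP. The Protocol establishes none of them.

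**The case for a change.** The strongest reply is that the Protocol hands over only the details of the boundaries, while it fixes the level and the interval itself. If the charter uses ordinary spending, the final level and its matching interval will differ from the 0.15 and 70% in Section 10.3.1. If it does not adjust, the error may exceed 15%. Only a very strict boundary leaves the text literally true for the last look, and none is required. A single sentence would settle the matter at no cost in patients.

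Part of this stands. The Protocol does not say that 0.15 is the overall level, and saying so would spare a reader the question. But it describes unstated detail, not a wrong rule. A boundary specification normally carries the alpha spent at each look and the level left for the end, and neither the charter nor the SAP was available here. The 70% interval does not show that the final test is unadjusted, because it equally describes an overall one-sided 0.15, and no decision hangs on it.

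One defence should not be leaned on. A continuity-corrected unstratified test would absorb the excess (simulated 0.116 and 0.132 with a mid-point look), but that is the test used for sizing, not the planned CMH test.

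**Conclusion.** No change to the plan is needed. The 0.15 level and the interim boundary are compatible as written, and dividing 0.15 between looks is a gap that a charter or SAP ordinarily fills.

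The size is bounded but conditional. With one look at 33% to 67% of the information and no adjustment anywhere, the overall one-sided error would be about 0.150 to 0.186 (up to 0.190 in the CMH simulation). With an O'Brien-Fleming-type boundary the excess is about 0.4 to 1.8 points, on a level chosen to be generous in a phase 2 signal-finding study. More looks or an unadjusted interim test would give more, but nothing in the text calls for either.

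The sample size also holds. The 129 participants and 80% power reproduce. Sharing 0.15 across one mid-point look would take the nominal 80% to 79.3% (O'Brien-Fleming-type) or 76.7% (Pocock-type), while the planned CMH test stays at 83% or more. The final level of 0.138 and the 72.4% interval illustrate one assumed design and are not corrections to this Protocol.

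This would be judged differently if the charter or SAP were found to spend a material part of alpha at an interim look and still run the final test at 0.15.
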